### 5.2.1.2 Dose Modification

The goal of this trial is to determine doses of IMI/REL for each pediatric age cohort that achieve similar therapeutic exposure parameters as seen in clinical trials in adults and have an acceptable safety profile. As such, all observed PK data will be entered into a rolling population PK model-based simulation. For each age cohort, the Sponsor will assess dose suitability during the planned interim reviews based on the observed PK and safety data from the first half of subjects enrolled into the cohort. The following parameters will be considered in determination of pediatric doses:

- Simulated population PK parameters for each age cohort approach the following values, as expected in adults:
  - Single-dose REL exposure of  $AUC_{0-\infty} \geq 37.5 \mu\text{M}\cdot\text{hr}$  (and  $\leq 200 \mu\text{M}\cdot\text{hr}$ ). Doses associated with this exposure have been established as being well tolerated in adults.
  - $\geq 30\%$  TMIC (within proposed dosing interval) for single-dose imipenem (and  $AUC_{0-\infty} \leq 250 \mu\text{M}\cdot\text{hr}$ ). Doses achieving these targets have been established as safe and efficacious in adults.

- Observed safety data demonstrates an acceptable safety profile, as defined by no life-threatening toxicities considered by the investigator to be related to study treatment. Life-threatening toxicities are defined as follows:
  - For laboratory AEs, a grade of 4 on the Division of Microbiology and Infectious Diseases pediatric toxicity scale [12].
  - For clinical AEs, events that are considered serious due to being life-threatening, as defined in Section 7.2.4 – Evaluating Adverse Events and as documented on the electronic case report form (eCRF).

Modified doses will not exceed the adult maximum of 500 mg IMI and 250 mg REL for a single IV dose, and dose modifications, if required, will be communicated to sites via Protocol Clarification Letters.

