1. The interim review revealed a suboptimal (ie, too high or too low) initial dose based on inadequate (ie, too high or too low) PK target attainment relative to adults for a given age cohort (details in Section 5.2.1.2 – Dose Modification), or
2. The safety profile was not acceptable.

Dose modifications following the interim reviews in Cohorts 1 through 3 are described in Section 5.2.1.2.1.

When enrollment of all 6 subjects each in Cohorts 1, 2, and 3 was completed, a second interim review was performed in which aggregated data from Cohorts 1, 2, and 3 was used to (1) develop and refine a pediatric population PK model and conduct simulations to evaluate PK target attainment, and (2) assess whether the safety profile was acceptable for each age cohort. The findings from the second interim review were used to inform the proposed initial doses for Cohorts 4 and 5, which is 10/5 mg/kg IMI/REL. Subject enrollment of Cohorts 4 and 5 was initiated in parallel.

For Cohorts 4 and 5, an interim review will be conducted in each age cohort after the first 4 (50%) subjects are enrolled in Cohort 4 and the first 9 (50%) subjects are enrolled in Cohort 5 (regardless of subcohort), at which point, enrollment in that cohort will pause.

Enrollment will continue past the fourth subject in Cohort 4 and the ninth subject in Cohort 5 without dose modification if the following occurs:

1. The interim review demonstrates that the selected initial dose is suitable based on PK target attainment that is similar to that in adults for a given age cohort (details in Section 5.2.1.2 – Dose Modification), and
2. The dose demonstrates an acceptable safety profile in the exposed cohort, as described in Section 5.2.1.2 – Dose Modification.

Alternatively, enrollment in each cohort will continue with a dose modification based on Section 5.2.1.2 – Dose Modification if the following occurs:

1. The interim review reveals a suboptimal (too high or too low) initial dose based on inadequate (too high or too low) PK target attainment relative to adults for a given age cohort (details in Section 5.2.1.2 – Dose Modification), or
2. The safety profile is not acceptable.

When enrollment into Cohorts 4 and 5 has been completed, a final analysis of PK and safety data will be performed with aggregated data from Cohorts 1 through 5 to refine the optimal dosing for pediatric subjects based on PK target attainment and an acceptable safety profile.

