- PK profiles of REL, imipenem, and cilastatin in healthy Japanese subjects were similar to historical data obtained from non-Japanese subjects.
- PK data from a study of renal-impaired subjects (PN005) were consistent with expectations given that REL, imipenem, and cilastatin are cleared almost entirely renally in healthy subjects. Plasma clearance, terminal half-life ( $t_{1/2}$ ), and  $AUC_{0-\infty}$  were significantly and similarly altered for each of these 3 analytes when comparing subjects with renal impairment to their healthy matched control subjects.
- REL and imipenem penetrate to a similar extent into the extracellular (epithelial lining fluid) of the lung.
- Supratherapeutic levels of REL had no impact on population-specific QTc.
- REL has low potential for any clinically meaningful drug-drug interactions.

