As treatment options are limited for MDR infections, and given that there are fewer antibiotics approved for use in pediatric patients as well as the dearth of clinical trials conducted in pediatric patients, the problem is even more critically important to address [9]. Carbapenems are the mainstay of treatment of MDR Gram-negative infections; therefore, the emergence of carbapenem-resistant organisms in recent years is particularly worrisome [10]. The addition of REL to IMI to restore IMI susceptibility for pathogens that produce class A and C  $\beta$ -lactamases therefore addresses an area of growing unmet medical need. Furthermore, IMI/REL is unique among  $\beta$ -lactam/BLI combinations in development due to the long history of pediatric safety and efficacy (Section 4.1.4 – Imipenem/Cilastatin Clinical Experience in Pediatric Populations) and the broad spectrum of activity of the  $\beta$ -lactam compound.

The current United States (US) Food and Drug Administration guidance document for pediatric PK studies focuses on appropriate dosing in the pediatric population based on PK data [11]. The PK of a drug in the pediatric population usually cannot be precisely predicted from PK or clinical studies of adult subjects; rather, specific PK studies in pediatric subjects are needed to determine appropriate pediatric dosing. Thus, the current study will be conducted to investigate the PK and safety of a single IV dose of IMI/REL in pediatric subjects from birth to <18 years of age receiving standard-of-care antibacterials for treatment of confirmed or suspected Gram-negative bacterial infection. The current study will be conducted using 5 age cohorts, with the predominance of subjects in the youngest age cohort, in accordance with guidance from the Food and Drug Administration and the European Medicines Agency (EMA). The information from this study will be used to determine appropriate dosing regimens for a subsequent efficacy study of IMI/REL in a pediatric population.

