### 5.2.1 Dose Selection/Modification

#### 5.2.1.1 Dose Selection (Preparation)

[Table 2](#) displays the proposed initial doses of the study drug for each age cohort. The proposed initial doses may be modified as described in Section 5.2.1.2 – Dose Modification. The dose modifications for Cohorts 1 through 4 that occurred as a result of the first interim review in these cohorts (ie, after 50% enrollment; see Section 8.7) are described in Section 5.2.1.2.1, along with the results of the second interim review (ie, following completion of enrollment in Cohorts 1 through 3) that led to the initial doses for Cohorts 4 and 5.

Table 2 Imipenem/Cilastatin/Relebactam (IMI/REL) Doses by Age Cohort

Age Cohort	Age Range	IMI/REL Proposed Initial Dose a
1 (n=6)	12 to <18 years	15/7.5 mg/kg over 30 min
2 (n=6)	6 to <12 years	15/7.5 mg/kg over 30 min
3 (n=6)	2 to <6 years	15/7.5 mg/kg over 30 min
4 (n=8)	3 months to <2 years b	10/5 mg/kg over 60 min c
5 (n=18)	Birth to <3 months d	10/5 mg/kg over 60 min c

Abbreviations: IMI/REL: imipenem/cilastatin/relebactam; TBD: to be determined

a The proposed initial doses may be modified based on interim data as described in Section 5.2.1.2 – Dose Modification. The dose modifications for Cohorts 1 through 4 that occurred as a result of the first interim review in these cohorts are described in Section 5.2.1.2.1. Single IV doses for all cohorts will not exceed the adult maximum dose of 500 mg IMI and 250 mg REL.

b At least 4 subjects in Cohort 4 will be <1 year of age.

c Initial doses of IMI/REL for subjects in Cohorts 4 and 5 were selected based on PK modeling and simulation analyses, after incorporating observed PK data from Cohorts 1 through 3 (Section 5.2.1.2.1). Initial doses for Cohorts 4 and 5 were communicated to sites via a Protocol Clarification Letter.

d Cohort 5 will be further subdivided into the following 3 age subcohorts:

- 4 weeks to <3 months of age; at least 6 subjects
- 1 to <4 weeks of age; at least 6 subjects
- <1 week of age; at least 6 subjects

The rationale for selection of doses to be used in this trial is provided in Section 4.0 – Background & Rationale. Additional details for preparation and administration of study drug are provided in a separate Pharmacy Manual.

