#### **5.2.1.2.1 Dose Modifications and Decisions After Interim Reviews**

At the time of this protocol amendment (-02), enrollment into Cohorts 1 through 4 has been completed. As planned, protocol-defined interim reviews of safety and PK data were completed for the first 50% of subjects in each age cohort. The dose modifications that were made as a result of the interim reviews are shown in [Figure 2](#). These dose modifications were communicated to sites via Protocol Clarification Letters and are based on the following considerations:

[figure not shown]
- At time of enrolling Cohorts 1 through 3, no pediatric-specific population PK model for imipenem and REL was available; therefore, PK endpoints from these cohorts were estimated based on an allometrically-scaled adult population PK model. The interim reviews in each cohort showed that the scaled adult model appropriately described the observed imipenem and REL concentrations from pediatric subjects in Cohorts 1 through 3.
- Cohort 1: At the initial dosing guidance of 15/7.5 mg/kg IMI/REL as a 30-minute IV infusion, all subjects received the full adult dose of 500/250 mg IMI/REL based on their weight. Based on modeling, likely weights of subjects in the age cohort would almost always necessitate the full 500/250 mg dose of IMI/REL; therefore, the dosing regimen was simplified to a flat single dose of 500/250 mg IMI/REL administered as a 30-minute IV infusion for the remaining subjects of Cohort 1.
- Cohort 2: Simulations showed that by increasing the study drug infusion duration from 30 minutes to 60 minutes at the proposed initial dose of 15/7.5 mg/kg IMI/REL, >90% of subjects in this age cohort would meet the protocol-defined safety targets, and ~ 75% of subjects in this age cohort would meet PK targets for both imipenem and REL. Therefore, the dosing regimen was changed to 15/7.5 mg/kg IMI/REL as a 60-minute intravenous infusion for the remaining Cohort 2 subjects in order to ensure the majority of patients met the safety and PK targets.
- Cohort 3: Simulations showed that by infusing IMI/REL at 15/7.5 mg/kg over 60 minutes (rather than over 30 minutes), ~98% of subjects in this age cohort would meet the protocol-defined safety targets for both imipenem and REL. Furthermore, a change in the infusion period from 30 minutes to 60 minutes was consistent with the

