updated regimen for the remaining subjects in Cohort 2. Therefore, the dosing regimen was changed to 15/7.5 mg/kg IMI/REL as a 60-minute intravenous infusion for the remaining Cohort 3 subjects.

After completion of enrollment of Cohorts 1 through 3 (2 to <18 years of age), the protocol-defined interim review of aggregate safety and PK data from these 3 cohorts was conducted. The observed safety data for all 19 subjects who received IMI/REL demonstrated an acceptable safety profile. PK data from the 18 PK evaluable subjects were used to develop a pediatric-specific population PK model for imipenem and relebactam. In order to extrapolate the developed pediatric population PK model for the older cohorts (2 to <18 years of age) to Cohorts 4 and 5 (<2 years of age), an adjustment function was included to account for a lack of full renal maturation for the subjects in this age range. Simulations were conducted to project the initial doses for Cohorts 4 and 5. The dosing regimen specified in Table 2 for Cohorts 4 and 5 was selected based on drug exposures that were projected to provide optimal probability of safety and efficacy.

For Cohort 4, simulations from the interim review showed that infusing IMI/REL at 15/7.5 mg/kg (rather than 10/5 mg/kg) over 60 minutes would result in projected efficacy and safety targets similar to the evaluated initial Cohort 4 dose of 10/5 mg/kg. Furthermore, choosing a 15/7.5 mg/kg dose for the remaining 4 subjects enabled data collection over an expanded dosing range, and therefore supports population PK model optimization and future clinical use. Additionally, the 15/7.5 mg/kg dosing regimen of IMI/REL is consistent with the current PRIMAXIN®/TIENAM® (imipenem/cilastatin) dosing recommendations for pediatric patients, for which there is a long history of safe and efficacious use.

Figure 2 Dose Modifications for Cohorts 1, 2, 3, and 4 After Interim Reviews

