## **8.6 Statistical Methods**

### **8.6.1 Modeling & Simulation Methods for Pharmacokinetic Analyses**

Relebactam and imipenem data will be used to develop a pediatric population PK model by using previous adult data in the form of the adult population PK model, which will be continuously updated as pediatric PK data become available from each age cohort. Any missing postdose plasma concentrations will be treated as missing. Values below the limit of quantification will be assigned a value of zero. A nonlinear mixed effects modeling approach will be used for model building. A Modeling and Simulation Analysis Plan with further details on the methodology will be prepared and finalized before database lock and analysis of the data.

There will be no formal hypothesis testing. The target is  $AUC_{0-\infty} \geq 37.5 \mu\text{M}\cdot\text{hr}$  (and  $\leq 200 \mu\text{M}\cdot\text{hr}$ ) for REL and  $TMIC \geq 30\%$  (and  $AUC_{0-\infty} \leq 250 \mu\text{M}\cdot\text{hr}$ ) for imipenem. The goal of model-based simulations will be to derive a dosing regimen where these targets are jointly achieved in a proportion of pediatric subjects similarly covered in adults (~ 90% probability of target attainment) for each age cohort; hence, achieving these targets implies similar efficacy as that obtained in adults. An absolute (mg) or weight-based (mg/kg) dose, whichever is found most suitable for each age cohort, will be selected based on the simulation results.

For cilastatin, an NCA will be conducted to determine its PK parameters. Descriptive statistics will be provided for cilastatin PK parameters by age cohort.

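### The Cohort 5 dose rule is set for birth to <3 months as a whole, so a cohort figure near the ~90% goal can hide relebactam over-exposure in neonates <1 week

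*Combined protocol and SAP*

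**What the plan says.** - **Unit of the rule.** Section 5.2.1.2 asks that "Simulated population PK parameters for each age cohort approach the following values, as expected in adults". The values are a relebactam (REL) AUC of 37.5 to 200 µM·hr and, for imipenem, time above MIC of at least 30% with AUC no higher than 250 µM·hr.
- **Goal.** Section 8.6.1 wants these targets "jointly achieved in a proportion of pediatric subjects similarly covered in adults (~ 90% probability of target attainment) for each age cohort". The same section selects the dose, in mg or mg/kg, by age cohort, and section 8.7 applies any change to the rest of that cohort.
- **Subcohorts.** Table 2 (section 5.2.1.1) notes that "Cohort 5 will be further subdivided into the following 3 age subcohorts": <1 week, 1 to <4 weeks, and 4 weeks to <3 months, with at least 6 subjects each. They serve as enrolment minima; no attainment criterion or dose is attached to them.
- **Timing.** Under section 2.1 the interim review is triggered when "the first 9 (50%) subjects are enrolled in Cohort 5 (regardless of subcohort", so the first nine may have any age mix.
- **Renal clearance.** Section 4.1.2.2 reports that "REL, imipenem, and cilastatin are cleared almost entirely renally in healthy subjects". Appendix 12.3 gives lower limits of 20 (<1 week), 25 (1 to <2 weeks), 41 (2 to <6 weeks) and 47 (6 to <14 weeks) mL/min/1.73m². In the model used to project the Cohort 4 and 5 starting doses, "an adjustment function was included to account for a lack of full renal maturation for the subjects in this age range" (section 5.2.1.2.1).
- **Use of the result.** Section 4.2.1: "The information from this study will be used to determine appropriate dosing regimens for a subsequent efficacy study of IMI/REL in a pediatric population".

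**The concern.** At one mg/kg dose, AUC is dose divided by clearance. If clearance per kg rises steeply over the first three months, the youngest neonates have the highest exposure. An attainment figure averaged over the cohort can look satisfactory because the older infants do well, while a material share of neonates <1 week lies above the REL ceiling. The maturation function lets the model show this gradient, but the written rule does not act on it.

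The separate safety criterion in section 5.2.1.2 would not pick it up, because that criterion is the absence of related life-threatening toxicity and is not triggered by exposure above the ceiling. Nor can a longer infusion correct it, since infusion time does not change AUC under linear kinetics.

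At stake are the dose given to the remaining <1-week subjects and the exposure information on the youngest that is carried into regimen selection for the efficacy study.

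**Working it through.** The plan's ~90% cannot be reproduced: the population model, MICs, dosing interval and simulated ages and weights are not in the documents. What can be checked is how far a cohort figure near 90% constrains the youngest stratum. This is done for REL alone, since both its AUC limits are given.

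**Inputs.** AUC limits 37.5 and 200 µM·hr (5.2.1.2). CV of REL clearance 40% (8.9), so σ = √ln(1 + 0.4²) = 0.385. Clearance limits 20, 25, 41, 47 (Appendix 12.3), giving a largest ratio of 47/20 = 2.35. *Assumed:* log-normal AUC, linear kinetics, and typical AUC at a fixed mg/kg dose inversely proportional to the limit. Smaller spreads R use the same shape on the log scale: AUC relative to the oldest stratum = (47/limit)^(ln R / ln 2.35).

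**One homogeneous stratum.** With typical AUC m, attainment = Φ(ln(200/m)/σ) − Φ(ln(37.5/m)/σ). The maximum is 97.0% at m = √(37.5 × 200) = 86.6. It is at least 90% for m from 61.6 to 121.8, a 1.98-fold range. At a 2.35-fold spread, no single mg/kg dose can reach 90% in both the youngest and the oldest stratum.

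**Cohort 5 as a mixture.** The simulated age mix is not stated, so two weightings are shown:
- *Even ages over 13 weeks:* weights 1/13, 1/13, 4/13, 7/13 for limits 20, 25, 41, 47.
- *Equal thirds (6/6/6), ages even within each subcohort:* weights 1/3, 1/9, 8/27, 7/27.

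Worked case, 2.35-fold, even ages. The best cohort figure is at an oldest-stratum typical AUC of 72.8. The <1-week typical AUC is then 72.8 × 47/20 = 171, and the share above 200 is 1 − Φ(ln(200/171)/0.385) = 34%. Attainment by stratum is 65.8%, 83.8%, 96.9% and 95.3%, so the cohort figure is (65.8 + 83.8 + 4 × 96.9 + 7 × 95.3)/13 = 92.6%.

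| Spread | Age mix | Best cohort attainment | <1 week above 200 at that dose | <1 week above 200 at highest dose with cohort ≥90% |
|---|---|---|---|---|
| 1.5 | even | 96% | 9% | 31% |
| 1.75 | even | 95% | 16% | 40% |
| 2.0 | even | 94% | 23% | 48% |
| 2.35 | even | 93% | 34% | 56% |
| 1.5 | thirds | 95% | 5% | 19% |
| 1.75 | thirds | 94% | 8% | 21% |
| 2.0 | thirds | 92% | 11% | 20% |
| 2.35 | thirds | 88.5% | 16% | 90% not reachable |

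**Sensitivity to CV (2.35-fold, best dose).** At CV 30%, the cohort figure is 96% with 22% above the ceiling in <1 week (even ages). At CV 50%, it is 88% with 39% above (even ages) and 83% with 21% above (thirds).

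**What a subcohort dose could do.** Matching typical AUC to the oldest infants means a <1-week dose lower by 1 − 1/1.5 = 33% to 1 − 20/47 = 57%. REL attainment could then approach the 97% maximum in each subcohort.

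**Data at the review.** If 18 subjects (6/6/6) arrive in random order, P(at most one <1-week subject in the first nine) = [C(12,9) + 6·C(12,8)]/C(18,9) = 3190/48620 = 7%. With independent arrivals at equal rates it is 14%. If <1-week subjects arrive at half the rate of each other subcohort (an assumption; p = 0.2), it is 44%.

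**The case against.** **The size depends on inputs the plan does not give.** A reader might infer that about one third of neonates <1 week would be over-exposed. The documents do not support that as a finding: it needs even ages over 13 weeks, the full 2.35-fold spread and CV 40% together. The only stated mix is the 6/6/6 enrolment minimum. With equal thirds a true 90% caps the <1-week failure rate at 3 × 10% = 30%, and the modelled excess is lower. This stands, so only ranges are given.

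**2.35 is not a clearance ratio per kg.** The Appendix 12.3 values are lower eligibility bounds per 1.73 m², while the dose is per kg, so the spread may well be smaller. Against infants of 4 to <6 weeks the ratio is 41/20 = 2.05. This also stands. At 1.5-fold and the best dose the problem is modest, with 9% or 5% above the ceiling.

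**There is no mechanical pass mark.** The ~90% is a goal, and 5.2.1.2 asks only that values approach the targets. Section 5.2.1.2.1 shows judgement in use: the Cohort 2 regimen was adopted when simulations projected roughly "75% of subjects in this age cohort would meet PK targets for both imipenem and REL". This is right, but it leaves the protection of the youngest to an unwritten tolerance.

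**Imipenem is left out.** Its ceiling could force a lower dose and fewer REL exceedances, so the REL-optimal dose need not be the one selected. This cannot be settled from the documents.

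**It may be handled elsewhere.** The maturation function makes the gradient visible, nothing forbids a dose by subcohort, and the Modeling and Simulation Analysis Plan may specify the age mix. However, 8.6.1 requires that plan before database lock and does not say that it governs the interim reviews.

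**Conclusion.** The concern holds as a gap in the decision rule. Suitability, the ~90% goal, the selected dose and any modification are all set at cohort level. In Cohort 5 that level spans a renal gradient shown by the protocol's own limits, and no subcohort check is written.

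For REL alone, with CV 40% and a 1.5- to 2.35-fold spread, the share of <1-week neonates above 200 µM·hr at the best cohort dose is about 9–34% (even ages) or 5–16% (equal thirds). At the highest dose still giving a cohort figure of 90%, it is 31–56% (even ages) or about 19–21% (equal thirds, spread 1.5- to 2.0-fold; at 2.35-fold no dose reaches 90%). That the answer changes this much with an unstated age mix is part of the point.

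Three further inferences would go too far. The figures do not show that 10/5 mg/kg over-exposes neonates, because no typical AUC at that dose is given. The plan's silence on subcohort dosing is not a prohibition. The interim dose does not bind the later regimen, since section 2.1 plans a final analysis of Cohorts 1 to 5 to refine dosing. The point is an inexpensive improvement worth making before the Cohort 5 review.

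**What to change.** Amend sections 5.2.1.2 and 8.7 before the Cohort 5 interim review:

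1. Refer to the ~90% goal of 8.6.1. For Cohort 5, report and judge it, including both AUC ceilings, separately in the three subcohorts. State the simulated age mix for any whole-cohort figure.
2. State that the mg/kg dose may differ by subcohort, keeping the 2:1 ratio. If an AUC limit fails in one subcohort, change the mg/kg dose there, not the infusion time.

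Optional: take the review at 3 subjects per subcohort (still 9 in all), or look again at the <1-week dose once 3 such subjects are available. Waiting for 3 in each subcohort could delay the review if the youngest enrol slowly, so items 1 and 2 should not depend on it.

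The cost is a few sentences, tabulating the planned simulations by subcohort, and possibly more than one regimen within Cohort 5. No extra subjects are needed.
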